4.2.5. Handling of Partial and Missing Death Date

Incomplete dates of death will be imputed as follows:

If only ‘day’ is missing, then impute with the first day of the month.

If ‘day’ and ‘month’ are missing and ‘year’ is not missing and is the same as the year of the last contact date, then impute as the date of the last contact +1 day.

If ‘day’ and ‘month’ are missing and ‘year’ is not missing and is greater than the year of the last contact date, then impute as 1st January of that year.

If the imputed death date is less than the last contact date, then set to the last contact date + 1 day.

4.2.6. Handling of Partial and Missing Diagnosis Date

The partial start date for initial diagnosis will be assigned to 15th day of the month (if only day is missing) or July 1st (if both month and day are missing).

For completely missing dates no imputation will be performed.

4.2.7. Handling of Partial and Missing Laboratory Data

Missing laboratory data will not be imputed. However, laboratory values of the form of “< x” (i.e., below the lower limit of quantification) or “> x” (i.e., above the upper limit of quantification) will be imputed as “x” for the purpose of calculation of summary statistics and comparing to normal ranges. These values will still be displayed as “< x” or “> x” in the listings.

4.2.8. Handling of Serum PK Concentrations for Study Treatment that are Below the Lower Limit of Quantification

Serum PK concentrations for Study Treatment that are Below the Lower Limit of Quantification (BLQ) will be handled as follows for descriptive statistics:

- For individual data listings, values that are BLQ (*add actual BLQ for nanrilkefusp alfa and cetuximab in ng/mL here*) will be reported as < LLOQ where LLOQ will be replaced by the actual value for LLOQ for the specific PK assay.
- Values that are BLQ will be set to 0 for the calculation of summary statistics by treatment at each scheduled time point (number of patients in analysis set (N), number of patients with data available (n), arithmetic mean, geometric mean, arithmetic SD, geometric coefficient of variation (%CV), 95% confidence interval (CI), median, min, and max).
- If there are less than 3 quantifiable values in a data series, only the minimum, maximum and n will be presented. The other summary statistics will be denoted as not calculated (NC).

- BLQ results (treated as 0) are in a series of summarized data, geometric mean and CV% will be reported as NC.
- Arithmetic mean or median values that are BLQ presented as 0.
- If a *predose* concentration is missing prior to the first dose of Cycle 1 Day 1, the values will be set to zero.

5. Statistical Methods

5.1. General Principles

All data processing, summarization and analyses will be performed using Fortrea's SAS Environment / Version 9.4 (or later) of the SAS® statistical software package.

The analyses will be descriptive; no formal testing of statistical hypotheses is planned.

Summary statistics:

The default summary statistics for quantitative variables will be the number of observations (n), mean, Standard Deviation (SD), median, minimum (min) and maximum (max), for those patients with data. For qualitative variables, the number (n) and percentage (%) of patients with non-missing data per category will be the default summary presentation, and where appropriate and present, the number of missing values as a "Missing" category. Number of patients in the analysis population will be used as denominator for percentages calculation, unless stated otherwise in TFLs.

Time-to-event endpoints will be summarized using Kaplan-Meier (KM) method. Estimation of median time and the associated 95% Confidence Interval (CI) will be provided using log-log transformation. Number of events, number of censored patients and descriptive statistics [25th and 75th percentiles, minimum and maximum] for time-to-event endpoints will be also provided. The KM curves will be graphically displayed.

Time conversion:

The following conversion factors will be used to convert days into months or years:

1 week = 7 days, 1 month = 30.4375 days, 1 year = 365.25 days.

Laboratory data:

All laboratory clinical safety and urine test results will be received from the local laboratories, and the results will be provided in both Standard Internal (SI) and conventional units. For the TFLs, the results will be summarized or presented in International System of Units (SI) units. Refer to Appendix of the TFLs mock shells for the SI unit corresponding to each laboratory test. Biomarkers, inflammatory cytokines and PK/ADA results will be received from the central laboratories.

Tables, Figures, and Listings (TFLs):

In the listings, laboratory values converted from conventional to International System of Units (SI) units will be reported to the same precision as values originally recorded as SI. Derived values for change/ percent changes in target lesions, and all safety endpoints will be rounded with one decimal place.

Refer to Appendix of the TFL shells for the precision level in which each laboratory test is reported by the central laboratories.

Specifications for table, figures and data listing formats can be found in the TFL shells specifications for this study. Please refer to “2. General Format Guidelines” section within TFL shells for more details on presentation of results.

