4.1. Time Points and Visit Windows

4.1.1. General Definitions

The study treatment defined is the combination of nanrilefusp alfa 9 µg/kg or 12 µg/kg subcutaneously and 400 mg/m² or 250 mg/m² cetuximab IV infusion.

All assessment days will be related to the first day of first dose of study treatment. Start of study treatment is defined as the date and time of first dose of either nanrilefusp alfa or cetuximab, whichever occurs earliest. Per protocol this should be nanrilefusp alfa.

General Definition	nanrilefusp alfa	Cetuximab
Study Day 1	Day 1 is the first dose of study treatment . Relative days after Day 1 are calculated as (assessment date – Day 1 date) + 1. Relative days prior to Day 1 are calculated as (assessment date – Day 1 date). The day prior to Day 1 is Day -1. Day 0 is not defined.	
Date of the First Dose	As per Exposure CRF (First date from Administration date) Minimum of first dose of nanrilefusp alfa and start date of the infusion for the first dose of cetuximab	As per Exposure CRF (First date from Administration date)
Date of the Last Dose	As per Exposure CRF (Last date from Administration date) Maximum of last dose nanrilefusp alfa and end date of the infusion for the last dose of cetuximab.	As per Exposure CRF (Last date from Administration date)
Treatment Cycle		As per CRF
Treatment Day		As per CRF
Change from baseline		Visit value – baseline value
Percentage change from baseline		100 * (visit value – baseline value) / baseline value

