5.4.2. Baseline Characteristics

Baseline characteristics will be summarized for the ASaT as described below. All missing data will be presented as part of a missing category, if appropriate.

Standard descriptive statistics will be presented for the continuous variables of:

- Height (cm) at baseline
- Weight (kg) at baseline
- BSA (m²) at baseline
- Body Mass Index (BMI) (kg/m²) at baseline, derived as Weight (kg) at baseline/Height² (cm²) at baseline
- Eastern Cooperative Oncology Group (ECOG) at baseline

No formal tests of statistical significance will be performed on the demographic and baseline characteristics data.

Baseline Characteristics analyses will also be repeated in the Efficacy Population as well as the Per Protocol Population.

Baseline characteristics will be listed for the screened population.

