5.6.4. Laboratory Evaluations

Data for the following coagulation, hematology, and biochemistry analytes received from local laboratory are to be measured at the scheduled visits indicated in the study flowchart.

All parameters recorded in the study will be included in the listings, but only parameters defined in

[Table 7](#) specifies the tests that will be included in the summaries.

Table 7 Laboratory Tests to Be Included in Summaries

Hematology Test (SI unit)	Biochemistry Test (SI unit)	Coagulation

○ Hemoglobin (g/L)○ Differential WBC ($10^9/L$ and %)
• Neutrophils• Lymphocytes○ Absolute lymphocyte count○ Platelet count ($10^9/L$)	
○ Alanine aminotransferase (ALT) (U/L)○ Aspartate aminotransferase (AST) (U/L)○ Total Bilirubin (mmol/L)○ Lactate Dehydrogenase○ Alkaline phosphatase (U/L)○ C-reactive protein○ Albumin (g/L)○ Creatinine (mmol/L)○ Creatinine Clearance (mL/s)	
○ D-dimer

All laboratory data will be reported in SI units. All quantitative laboratory test values at each assessed visit will be compared with the relevant reference range in SI units and categorized as:

Low: Below the lower limit of the reference range.

Normal: Within the reference range (upper and lower limits included).

High: Above the upper limit of the reference range.

For analysis purposes, values preceded by a “ $<$ ” or a “ $>$ ” sign (i.e. those below or above the limits of quantification) will be considered equal to the lower or upper limit of quantification, respectively.

Laboratory data will be summarized by default descriptive summary statistics for continuous and categorical variables for the ASaT population by overall as follows:

- Observed values and change from baseline at each scheduled assessed visit for each standard continuous laboratory parameter

Listings of all clinical laboratory data including derived change from baseline will be provided for the screened population. Within each listing, laboratory values outside the normal ranges will be flagged as either high or low for applicable laboratory assessments.

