5.6.5. Hy's Law for Liver Function Tests

Hepatic function abnormality defined by an increase in AST and/or ALT to $\geq 3 \times \text{ULN}$ concurrent with an increase in total bilirubin to $\geq 2 \times \text{ULN}$ but without increase in alkaline phosphatase (i.e., alkaline phosphatase $< 2 \times \text{ULN}$) meets the criteria for Hy's law and raises the concern for drug-induced liver injury when no other cause is identified.

The summary of liver function tests will include the following categories, and the number and percentage of patients meeting Hy's Law at each scheduled visit during the on-treatment period will be summarized for ASaT population.

An eDISH figure displaying patients who reach $3 \times \text{ULN}$ for ALT or AST, plus $2 \times \text{ULN}$ for total bilirubin and thus are at risk for a drug induced liver injury according to Hy's law will be presented for ASaT population. A listing of patients at risk will also be presented for screened population.

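### As written, the SAP's mmol/L units and one-decimal rule make bilirubin and creatinine changes from baseline largely uninformative, and its BMI formula uses cm² under a kg/m² label

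*SAP*

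**What the plan says.** SAP 5.6.4, Table 7, names the laboratory tests to be summarised and gives units for most of them. Two entries matter here: "Total Bilirubin (mmol/L" and "Creatinine (mmol/L", each closing its bracket after the unit. The summary for these tests is "Observed values and change from baseline at each scheduled assessed visit for each standard continuous laboratory parameter". SAP 4.1.1 defines change from baseline as "Visit value – baseline value", an absolute difference in the reported unit. No percentage change is planned for laboratory tests. The laboratory listings in SAP 5.6.4 also carry the derived change.

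SAP 5.1 sets the precision: "Derived values for change/ percent changes in target lesions, and all safety endpoints will be rounded with one decimal place". It makes no exception for laboratory changes. The same section refers the reader to the table, figure and listing (TFL) shells for the SI unit of each laboratory test, and for the precision at which central laboratories report each test.

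SAP 5.4.2 lists "Body Mass Index (BMI) (kg/m²) at baseline, derived as Weight (kg) at baseline/Height² (cm²) at baseline".

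**The concern.** Serum bilirubin and creatinine are small numbers in mmol/L. A display step of 0.1 mmol/L is coarse against the changes one would want to see, so a table that follows both rules would show 0.0 for many of them. These are two of the few biochemistry tests chosen for summary. The liver is also a named area of concern: Hy's law cases count as DLTs (Protocol 4.1.2), and Protocol Table 6.2 is built on bilirubin bands at 1.5 and 3 x ULN. At stake is whether the change columns and listings for these tests carry usable information.

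The BMI formula is a separate matter. Its label and its divisor use different length units, so a programmer who follows the formula literally gets a wrong number whatever the rounding.

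**Working it through.** The plan states no figure to reproduce. The check is unit conversion and rounding.

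**Inputs from the documents**
- Unit mmol/L for both tests (SAP Table 7).
- One decimal for derived safety values (SAP 5.1).
- Absolute change (SAP 4.1.1).
- The Hy's law condition, "concurrent with an increase in total bilirubin to" 2 x ULN or more (SAP 5.6.5).
- The 3 x ULN upper edge of the grade 2 bilirubin band (Protocol Table 6.2).

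**Assumed inputs (not in the documents)**
- 1 mg/dL bilirubin = 17.104 µmol/L; 1 mg/dL creatinine = 88.42 µmol/L.
- Bilirubin ULN 1.0 to 1.4 mg/dL; normal baseline bilirubin from 0.3 mg/dL up to ULN.

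**Print threshold.** At one decimal, any change smaller than 0.05 mmol/L (50 µmol/L) in size prints as 0.0.
- Bilirubin: 50 / 17.104 = 2.92 mg/dL.
- Creatinine: 50 / 88.42 = 0.57 mg/dL.

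**Bilirubin.** Change (mmol/L) = (k x ULN − baseline) x 17.104 / 1000, with ULN and baseline in mg/dL.

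| Rise | Change, mmol/L | Prints |
|---|---|---|
| Baseline 0.3 mg/dL up to ULN, to 2 x ULN (ULN 1.0 to 1.4) | 0.017 to 0.043 | 0.0 in every case |
| ULN to 3 x ULN (ULN 1.0 to 1.4) | 0.034 to 0.048 | 0.0 in every case |
| 0.6 mg/dL to 3 x ULN (ULN 1.2) | (3.6 − 0.6) x 17.104 / 1000 = 0.0513 | 0.1 |
| Baseline 0.3 mg/dL up to ULN, to 5 x ULN (ULN 1.0 to 1.4) | 0.068 to 0.115 | 0.1 |

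**Creatinine.** Change (mmol/L) = rise in mg/dL x 88.42 / 1000.

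| Rise | Change, mmol/L | Prints |
|---|---|---|
| +0.3 mg/dL | 0.027 | 0.0 |
| +0.5 mg/dL | 0.044 | 0.0 |
| 1.5-fold from 0.6 to 1.0 mg/dL | 0.027 to 0.044 | 0.0 |
| 1.5-fold from 1.2 mg/dL | 0.053 | 0.1 |
| Doubling from 0.9 mg/dL | 0.080 | 0.1 |
| Tripling from 0.9 mg/dL | 0.159 | 0.2 |

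**BMI at 70 kg and 170 cm**
- As written: 70 / 170² = 70 / 28,900 = 0.0024.
- With height in metres: 70 / 1.70² = 70 / 2.89 = 24.2 kg/m².
- The ratio is 100² = 10,000 for every patient.

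**The same changes in µmol/L at one decimal**
- Bilirubin from 0.6 mg/dL to 2 x ULN (ULN 1.2): (2.4 − 0.6) x 17.104 = +30.8.
- Creatinine +0.5 mg/dL: 0.5 x 88.42 = +44.2.

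Both print as 0.0 under the present rules.

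**The case against.** The strongest reply is that SAP 5.1 leaves both units and laboratory precision to the TFL shells, which are not available here and may already solve the problem. That stands as a limit on certainty, but it does not remove the point. Table 7 states the unit itself. The precision reference concerns tests reported by central laboratories, whereas safety tests are local (Protocol 8.2.5; SAP 5.1 and 5.6.4). It also concerns reported results, not derived changes. If the shells differ from the SAP text, the two still need to be aligned.

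A second reply is that the rounding sentence follows one about listings and may govern listings only. On that reading the listings are still affected, because they carry the derived change, and the summary tables are left without a stated precision for it.

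A third is that the unit could be a misreading of µ as m in the text of the SAP. This cannot be excluded entirely, but µ appears correctly elsewhere in the SAP, for example in the µg/kg doses. The BMI point does not depend on it.

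A reader might also infer more than the documents support:
- **That hepatic safety could not be assessed.** SAP 5.6.5 gives Hy's law counts by visit in multiples of ULN, an eDISH figure and a listing of patients at risk. SAP 5.6.4 gives observed values, high and low flags, and boxplots with reference limits for selected parameters. SAP 5.6.3 gives adverse events by CTCAE grade. None of these depends on the rounding of derived changes.
- **That every important rise would show as 0.0.** The tables above show several that print 0.1 or 0.2.
- **That the 3 mg/dL bilirubin limit in Protocol 5.1, about 0.051 mmol/L, is hidden by the rule.** It is an eligibility level, not a change from baseline.
- **That BMI would print as 0.0.** The one-decimal rule does not clearly cover a baseline characteristic. The formula is wrong at any precision.

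**Conclusion.** The point holds as a minor reporting defect. If the SAP is followed as written, bilirubin changes below about 2.9 mg/dL and creatinine changes below about 0.57 mg/dL appear as 0.0 in the change-from-baseline output, and larger ones appear only in steps of 0.1 mmol/L. The hidden range includes a bilirubin rise from a normal baseline to the SAP's own Hy's law level, and a rise from ULN to 3 x ULN. BMI as derived is too small by a factor of 10,000.

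The thresholds rest on standard conversion factors, and the bilirubin examples also on a ULN of 1.0 to 1.4 mg/dL; none of these is in the documents. The conclusion also assumes that the shells do not override the SAP text. The defect does not reach patient-level safety detection, the DLT assessment, the futility rule or the primary ORR. BMI is a descriptive baseline item that enters no other analysis in the SAP.

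**What to change.** Three wording changes in the SAP, with the shells brought into line:

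1. In Table 7, state total bilirubin and creatinine in µmol/L. Alternatively, keep mmol/L and set the number of decimals by analyte for derived laboratory changes.
2. In SAP 5.1, say that derived laboratory changes follow the precision set for each analyte and not a flat one decimal. Correct the precision reference so that it covers local laboratory results, and check that the TFL shells carry the same units and decimals.
3. In SAP 5.4.2, derive BMI as weight (kg) / (height (cm) / 100)².

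The cost is editorial, plus a check of the programming specifications. No new data, visits or analyses are needed.

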5.2. Patient Disposition and Data Sets Analyzed

Patient disposition will be summarized by cohort and overall, where appropriate, for the screening population on assigned treatment. The following information will be reported:

- Number and percentage of Screen Failure patients with the reason;
- Number and percentage of patients for the following categories:
 - Enrolled ,
 - Treated ,
 - Not Treated ,
 - Discontinued study treatment (nanrilkefusp alfa, cetuximab, or both),
 - Reasons for study treatment discontinuation,
 - Ongoing in the study,
 - Completed the study,
 - Discontinued the study,
 - Reasons for study discontinuation.
- Number and percentage of patients included in, and excluded from efficacy population, PP population, and PK population together with the reasons for exclusion from the population;
- Number and percentage of patients at each country/site (ASaT population using assigned treatment will be used for this summary);

A patient will be regarded as having completed the study if the Reason for Completion/Discontinuation on the End of Study eCRF form is “Study completed as per Protocol”. A patient will be considered as having discontinued the study if Reason for Completion/Discontinuation is not “Study completed as per Protocol” and not Missing study discontinuation. Otherwise, the patient will be considered as ongoing study. The date of 'End of Study eCRF form' will be used for the definition of end of study date. In case a patient is death the date needs to be equal to Death Details eCRF form is “What was the subject’s date of death?”.

A listing of all patients with their treatment and study completion status, including the respective reasons for treatment and study discontinuation will be presented for the enrolled population.

A listing of all screen failed patients with their reasons for screen failure will be presented for the screening population. A separate listing of patients who failed at least one

inclusion/exclusion criteria including a text description of the criterion failed will be presented for the screening population.

A listing of all patients excluded from efficacy population, PP population or pharmacokinetics population will be presented for the enrolled population.

5.3. Protocol Deviations

All important protocol deviations leading to exclusion from the PP Population (see [Section 3.5.1](#)) will be summarized for the ASaT population overall as described below:

- The number of unique patients with at least one important protocol deviation which led to exclusion from the PP Population as well as the number of patients in each important protocol deviation category will be presented by default descriptive summary statistics for categorical variables.

A listing of all patients with one or more important/non important protocol deviations will be presented for the enrolled population. In addition, a listing of the patients affected by Coronavirus Disease of 2019 (COVID-19) and the type of COVID-19 disruption will be provided for the enrolled population, if applicable.

5.4. Demographic and Other Baseline Characteristics

5.4.1. Demographic Characteristics

Demographic characteristics will be summarized for the ASaT population as described below. All missing data will be presented as part of a missing category, if appropriate. Standard descriptive statistics will be presented for the continuous variables of:

- Age (years)

Total counts and percentages of patients will be presented for the categorical variables of:

- Age group (years):
 - < 18
 - >= 18 to < 65
 - >= 65 to < 85
 - >= 85
- Sex
 - If female, Childbearing potential (Yes/ No)
 - If No, Reasons
- Race
- Ethnicity

Demographic Characteristics analyses will also be repeated in the Efficacy Population as well as the Per Protocol Population and listed for the screened population.

5.4.2. Baseline Characteristics

Baseline characteristics will be summarized for the ASaT as described below. All missing data will be presented as part of a missing category, if appropriate.

Standard descriptive statistics will be presented for the continuous variables of:

- Height (cm) at baseline
- Weight (kg) at baseline
- BSA (m²) at baseline
- Body Mass Index (BMI) (kg/m²) at baseline, derived as Weight (kg) at baseline/Height² (cm²) at baseline
- Eastern Cooperative Oncology Group (ECOG) at baseline

No formal tests of statistical significance will be performed on the demographic and baseline characteristics data.

Baseline Characteristics analyses will also be repeated in the Efficacy Population as well as the Per Protocol Population.

Baseline characteristics will be listed for the screened population.

5.4.3. Cancer History

Cancer History analyses will be summarized for the ASaT.

Standard descriptive statistics will be presented for the continuous variables of:

- Initial diagnosis to Screening: time from initial diagnosis of cancer to screening defined as screening date – initial diagnosis date + 1.
- Initial diagnosis to start of treatment: time from initial diagnosis of cancer to first dose defined as First dose date – initial diagnosis date + 1.
- Metastatic diagnosis to start of treatment: time from metastatic diagnosis to first dose defined as First dose date – metastatic disease date + 1.
- Latest disease progression to start of treatment: time from latest disease progression to first dose defined as First dose date – latest disease progression date + 1.
- Number of previous lines of therapy

Total counts and percentages of patients will be presented for the categorical variables of:

- Site of primary tumor and sites of metastatic disease
- Stage at study entry: primary tumor (T) stage, regional lymph nodes (N) stage, distant metastasis (M) stage, and staging

- Histology/ Cytology results and type
- Prior mutation/ Expression status of Kirsten rat sarcoma viral oncogene homolog (K-RAS), Neuroblastoma rat sarcoma viral oncogene homolog (N-RAS), V-raf murine sarcoma viral oncogene homolog B1 (BRAF) and EGFR
- Number of previous lines of therapy (continuous and categorical)
- Previous treatment with EGFR inhibitors
- Response of previous treatment with EGFR inhibitors

Cancer History analyses will also be repeated in the Efficacy Population as well as the Per Protocol Population.

Cancer History will be listed for the screened population.

